8 SAFETY ANALYSES

Adverse events (AE) will be processed by MedDRA coding with System Organ Class (SOC) and Preferred Term (PT) by a medical monitor. They will be evaluated further for severe adverse event (SAE) categorization. Adverse events will be summarized by tabulating the number and percentages of enrolled subjects experiencing each event through milestone time points. Device- and procedure-related adverse events will be summarized separately.

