#### 4.6 Loss to Follow-up Considerations

It is estimated that the overall general loss to follow-up will be 10% at the time of primary analysis, and a true loss to follow up rate <10% will incur censoring while a loss >10% will require various sensitivity analyses.

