### 5.5 Enrollment (Day 0)

Once any component of the LimFlow System is introduced into the body, the subject will be considered to be enrolled in the study. If any LimFlow device is introduced but stent-graft implantation is either not attempted or unsuccessful, subjects will be followed for safety for 30 days with a minimum of phone calls to assess Primary Endpoint of AFS.

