11.5 Statistical Analyses

11.5.1 General Approach

Descriptive statistics for continuous variables will include mean, standard deviation, median, quartiles, minimum, maximum, and sample size for each treatment group. Categorical variables will be summarized using counts and percentages. Proportions will be calculated using known non-missing values. Unless otherwise indicated, all statistical tests will be performed at  $\alpha=0.05$  (2-sided), and confidence/credible intervals will be at level 95%.

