2 SCOPE

This statistical analysis plan covers the analyses to be performed after enrolled patients reach the primary endpoint according to PROMISE II protocol (LF-CA-PR-3).

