The censoring mechanism applied to these simulated event times is induced by the accrual rates, the timing of analyses, and by a random dropout pattern. For every simulated subject, a study start time is assigned according to an assumed accrual pattern, and when an analysis occurs, such as the first sample size evaluation when 60 subjects have been enrolled, each simulated subject's event time is censored at that time (if an event has not previously occurred for that subject). In addition, a designated fraction of simulated subjects is randomly chosen to be lost to follow-up at random times that are uniformly distributed over their 180-day study period, and these subjects are censored at the minimum of the dropout time and the analysis time (assuming they have not yet had an event). For other analysis times (interim or final), censoring times are simply re-computed based on the new time of analysis, and some simulated subjects who did not have an event at the first sample size analysis may have events at a subsequent analysis.

Lost to Follow-up / Data Missingness

Simulations were conducted under the assumption of 10% lost to follow-up (LTFU) over the 6-month study period. With each simulated trial, each subject was designated to be "lost" with probability 0.10; thus, the exact number of subjects designated to be lost from one simulated trial to the next varied, though on average it was 10%. Furthermore, those subjects designated as "lost" were assumed to have been lost uniformly in time over the 6-month period. Subsequent to this, subjects were assigned event times. If the event time occurred after the LTFU time, that subject was considered censored at the LTFU time, whereas if the event time occurred before the LTFU time, that subject had an observed event at the event time.

Rate of Accrual

The speed at which subjects are recruited into the trial is an important assumption embedded within the simulations to determine operating characteristics. The expected rate of accrual into the analysis population is 5 subjects/month, after an initial ramp-up period for the first 7 months of 1, 2, 2, 3, 3, 4, and 4 subjects/month. This "expected" accrual rate was used in the generation of operating characteristics shown in Table 2.

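### SAP section 8 gives adverse events as percentages of enrolled subjects with no allowance for incomplete follow-up, which modestly understates 6-month rates

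*SAP*

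**What the plan says.** SAP section 8 plans one form of safety summary: "Adverse events will be summarized by tabulating the number and percentages of enrolled subjects experiencing each event through milestone time points", with device- and procedure-related events shown separately. It does not list the milestones or say how a subject whose observation ends before one is counted.

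Other sections fix the context:

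- **Who is enrolled.** Protocol 5.5: "Once any component of the LimFlow System is introduced into the body, the subject will be considered to be enrolled in the study". The same section gives subjects with no implanted stent graft 30 days of safety follow-up.
- **Exit.** Under Protocol 5.9 a subject leaves the study at major amputation or death.
- **Planned loss.** SAP 6.7: "Simulations were conducted under the assumption of 10% lost to follow-up (LTFU) over the 6-month study period". The lost subjects were "assumed to have been lost uniformly in time over the 6-month period". Protocol 4.6 also expects 10%, and says that "a true loss to follow up rate <10% will incur censoring while a loss >10% will require various sensitivity analyses".
- **Capture window.** Protocol 8.5 collects related adverse events and all serious adverse events to the 6-month visit, and index-limb serious adverse events to 3 years.
- **Timing.** SAP section 2: "This statistical analysis plan covers the analyses to be performed after enrolled patients reach the primary endpoint". SAP 6.4 holds the final analysis until every enrolled subject has had the opportunity for 180 days.
- **A different general rule.** Protocol 11.5.1: "Proportions will be calculated using known non-missing values".
- **Other endpoints.** SAP section 7 uses Kaplan-Meier methods for secondary events at 30 days or later. The primary analysis imputes missing 6-month outcomes.

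**The concern.** Read literally, the denominator is set on Day 0 and does not change. Events recorded before a subject is lost are counted; events after that cannot be, yet the subject remains in the denominator at every later milestone. The error has one direction: the reported rate is at or below the true rate.

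The trial has a single arm, so absolute adverse event rates are what a reader will take from the safety table, and there is no control arm in which a similar shortfall could partly cancel. The table as planned would not show how many subjects were still under observation, so its reader could not judge the size of the error. The primary and secondary endpoints do receive methods that deal with incomplete follow-up.

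**Working it through.** SAP section 8 states no adverse event rate, so there is no figure of its own to reproduce, and all true rates below are assumptions. The borrowed event-time shape was checked first: the hazards in SAP 6.7 give event-free survival of 0.850, 0.700, 0.620 and 0.540 at days 30, 60, 90 and 180, as stated there.

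**1. Loss to follow-up at 6 months.** Let *p* be the true 180-day rate, *d* the proportion lost, and *F(u)* the cumulative rate by day *u*. With loss times uniform over 180 days and unrelated to events:

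crude rate = (1 − *d*) × *p* + *d* × mean of *F(u)*

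Under a constant hazard the mean of *F(u)* is 1 − *p* / (−ln(1 − *p*)). For *p* = 0.30 this is 1 − 0.30/0.3567 = 0.159, so the crude rate is 0.9 × 0.30 + 0.1 × 0.159 = 0.286. With the SAP 6.7 hazards scaled to give *p* = 0.30 the mean is 0.202, so the crude rate is 0.27 + 0.0202 = 0.290.

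| Assumed true rate | Reads, SAP event timing | Reads, constant hazard | Shortfall (points) |
|---|---|---|---|
| 5% | 4.8% | 4.8% | 0.2 |
| 10% | 9.7% | 9.5% | 0.3 to 0.5 |
| 20% | 19.3% | 19.0% | 0.7 to 1.0 |
| 30% | 29.0% | 28.6% | 1.0 to 1.4 |
| 46% | 44.6% | 43.9% | 1.4 to 2.1 |

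At 30%, that is 1.0 to 1.5 subjects of 105. With 20% loss the shortfall over the same rates is 0.4 to 4.1 points. If all events fall in the first 30 days, it is 0.1 points at a true 10% and 0.2 points at a true 30% (10% loss).

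**2. Subjects followed for 30 days after no implant.** The documents give no expected number, so only a cost per subject can be shown. Assume the same hazard as other subjects and a 30% rate at 180 days. The rate by day 30 is then 1 − 0.70^(30/180) = 0.058 under a constant hazard, or 0.090 with the SAP timing. One such subject among 105 lowers the crude 6-month rate by (0.300 − 0.058)/105 = 0.0023 or (0.300 − 0.090)/105 = 0.0020, about 0.2 points.

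**3. Administrative cut-off.** SAP 6.7 assumes 1, 2, 2, 3, 3, 4 and 4 subjects in months 1 to 7 (19 in total), then 5 a month. Reaching 105 takes 86/5 = 17.2 further months, so the last subject enters at about month 24 and the 6-month lock is at about month 30. At that lock:

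| Milestone | Short of it, of 105 |
|---|---|
| 6 months | 0 |
| 9 months | 15 (14%) |
| 12 months | 30 (29%) |
| 24 months | 90 (86%) |

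**4. The known-status alternative.** If the Protocol 11.5.1 rule is taken to mean subjects with an event or followed to day 180, the denominator fraction is crude rate + (1 − *d*)(1 − *p*). For *p* = 0.30 under a constant hazard this is 0.286 + 0.9 × 0.7 = 0.916, and the rate reads 0.286/0.916 = 31.2%. With the SAP timing it reads 31.5%. That rule errs upward.

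**The case against.** The case for leaving section 8 alone has real force.

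- **The error at 6 months is smaller than sampling error.** At a true 20%, planned loss costs about one subject of 105, while the exact 95% interval for 21/105 runs from 12.8% to 28.9%. This stands, and it limits the severity.
- **The word enrolled may only name the population.** It matches the mITT set, and Protocol 11.5.1 points to a different denominator. A reader might infer that the SAP has firmly chosen an all-enrolled denominator over one that allows for follow-up. The documents show instead an unreconciled pair of rules, and the other rule is also biased.
- **Safety evidence exists elsewhere.** A reader might infer that this table is the only safety evidence. It is not: death and major amputation form the primary endpoint, with imputation and a tipping-point analysis, and limb salvage is a secondary endpoint. The point concerns the remaining adverse events.

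Two stronger readings of size should also be resisted. One is that later milestones are badly understated by design; a constant-hazard 30% at 24 months would read 21.1% from cut-off alone. Protocol 8.5 ends general collection at 6 months, and SAP section 8 nowhere says that 12- or 24-month percentages will be printed at the primary lock. The adverse event row in Protocol Table 1 is ticked to 3 years, but its footnote and Protocol 8.5 keep only index-limb serious events open that long.

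The other is to count exit at amputation or death as missing data. If adverse events are independent of exit with a constant hazard, and there is 10% loss, a 30% rate would read 23% with AFS of 0.70 and 20% with AFS of 0.54. That is an upper illustration only, because death truly precludes later events.

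**Conclusion.** The concern holds in a limited form. SAP section 8 makes no allowance for incomplete follow-up, and the resulting bias favours the device. Planned loss alone understates 6-month rates by 0.2 to 2.1 points for assumed true rates of 5% to 46%; subjects with only 30 days of follow-up add to this by an amount that the documents do not allow to be fixed. Cut-off contributes nothing at 6 months.

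These sizes assume uniform loss unrelated to adverse events, and event timing between the SAP's front-loaded shape and a constant hazard. Loss related to adverse events would change them. The severity is minor. The change is worth making because it is cheap and the table would otherwise hide how much follow-up lies behind each percentage.

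**What to change.** In SAP section 8:

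1. Name the milestones and keep the crude counts.
2. Add cumulative incidence (Aalen-Johansen) with 95% confidence intervals and number at risk: for serious adverse events and for device- or procedure-related adverse events at 30 days and 6 months, and for index-limb serious adverse events at any later milestone reported.
3. Treat death, and study exit at major amputation, as competing events. Censor at loss to follow-up, at the end of 30-day follow-up after no implant, and at data cut-off.
4. Do not print an enrolled-denominator percentage for a milestone that not all subjects could have reached.
5. State that this replaces the general rule of Protocol 11.5.1 for adverse events.

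The cost is SAP wording and a little programming. No new data, sample size change or alpha is needed. The reported safety percentages will be slightly less favourable.

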9 OTHER ANALYSES

9.1 Sensitivity Analyses for the Primary Endpoint

At the conclusion of the study, several planned analyses will assess sensitivity to certain analysis and data features.

9.1.1 Sensitivity to Missing Data

All reasonable efforts will be undertaken to minimize missing data. However, some missingness is inevitable, and the study is designed with the expectation that there may be up to 10% missing primary data at 6 months. The reasons for missing data will be described in detail and evaluated for assessment of possible bias.

By design, the analysis of the primary endpoint multiply imputes 6-month outcomes for any subjects without measured 6-month outcomes, based on available follow-up and the imputation model previously described (Section 6.5). Several additional analyses are planned that will explore the sensitivity of the main conclusions, specifically:

- A completers-only analysis of binary outcomes will be conducted. This analysis will exclude subjects with missing final primary outcome, presenting the posterior probability that $\phi > 0.54$ based on those subjects whose status is known at Day 180. The prior for ϕ will be Beta(1,1).
- A tipping-point analysis of binary outcomes will be conducted. This analysis will systematically consider each subject with missing outcome at Day 180 as an Event or a Non-Event at 180 days, in all combinations. Posterior probabilities (that $\phi > 0.54$) will be presented for each combination. The prior for ϕ will be Beta(1,1).
- A multiple-imputation analysis similar to the primary analysis will be conducted, only this sensitivity analysis will use a piecewise exponential prediction model with 6 pieces (rather than 4), with the time axis from 0 to 180 days partitioned such that there are approximately equal numbers of events in each piece. Specifically, if a total of V events are observed within $[0, 180 \text{ days}]$, the k^{th} piece ($k=1, \dots, 5$) in the partition will end with a cutpoint equal to the smallest integer day D such that $D \geq k \times V/6$. The 6th piece ends at 180 days.

9.1.2 Sensitivity to COVID-19 deaths

By definition (Section 1), AFS includes deaths documented to be caused by COVID-19. The following additional analyses are planned to assess sensitivity of the study's conclusions to the handling of deaths related to COVID-19.

- An analysis wherein all deaths due to COVID-19 are censored on the date of death.
- A tipping point analysis in which COVID-19 deaths are included, or not, in the definition of AFS, in every combination. This analysis will use the methods of Section 6 (similar to the principal analysis) but will

STATISTICAL ANALYSIS PLAN

conduct the imputation/prediction for subjects with missing final status as if they are similar to the cohort of subjects who did not die of COVID-19. In other words, if k subjects die of COVID-19, the parameters of the piecewise exponential model in Section 6.5 (the imputation model) will be estimated while removing the k subjects who died of COVID-19, but the final posterior probability will be computed by re-inserting the COVID deaths (in separate analyses) as follows:

- k COVID deaths count as deaths at Day 180.
- $(k-1)$ COVID deaths count as deaths at Day 180, 1 counts as a non-AFS event at Day 180
- $(k-2)$ COVID deaths count as deaths at Day 180, 2 count as a non-AFS event at Day 180
- Etc.
- 0 COVID deaths count as deaths at Day 180, k count as non-AFS events at Day 180
- A frequentist competing risk survival model in which deaths due to COVID-19 are considered competing risks. Cause-specific cumulative incidence functions (CIF) will be estimated, and confidence intervals for the CIF at 180 days will be reported. The levels of confidence will be 95% (two-sided) and 97.7% (one-sided, analogous to the Bayesian posterior threshold $\psi = 0.977$).
- Other analyses suggested by patterns of observed data may be conducted.

9.2 Subgroup Analyses for the Primary Endpoint

Descriptive statistics and Bayesian posterior distribution summaries (e.g., mean, median, 95% credible interval) will be computed for the amputation-free rate parameter ϕ when computed separately according to each of the subgroups defined below. Pre-specified subgroups are:

- Sex (Male/Female)
- Dialysis status (Yes/No)
- Age (≤ 70 , > 70)
- Diabetes (Type I, Type II, None)
- Race/Ethnicity
- Rutherford Classification

9.3 Demographic and Clinical Characteristics

Tables of baseline characteristics will be summarized using descriptive statistics. For continuous measures, the number of observations, mean, median, quartiles, minimum, and maximum will be reported for each measure. For categorical measures, the proportion, numerator, and denominator for each category will be reported.

Untreated subjects (see Section 5.3) will be described with similar descriptive statistics and with a listing.

The proportion of subjects screened and enrolled will be tabulated by site, along with measures of compliance to follow-up visits.

9.4 Tabulation of Individual Participant Data

Patient data listings, including demographics, baseline characteristics, safety data, adverse events, procedural data, and endpoints, will be provided.

9.5 Heterogeneity

Heterogeneity across sites will be assessed as follows. Based on completers, a (frequentist) Cox proportional hazards regression will be conducted, with a term for site included in the model. If there is not a significant site effect ($p > 0.10$), data will be considered poolable across sites. If there is a significant site effect ($p < 0.10$), an investigation will be conducted into whether subject baseline characteristics explain this difference. Candidate baseline characteristics include those that (1) significantly predict AFS, (2) significantly differ across sites, or (3) are deemed to be clinically important. If a baseline characteristic (or set of characteristics) explains the difference (in that inclusion of the characteristic(s) in the proportional hazards regression model causes the site effect to become non-significant, $p > 0.10$), a summary Bayesian analysis of AFS adjusting for the characteristic(s) will be conducted. If baseline characteristics do not explain the difference, results will be

STATISTICAL ANALYSIS PLAN

presented by site and in various groupings of sites as appropriate (e.g., perhaps removing any markedly different sites).

The summary Bayesian analysis will be a Bayesian piecewise exponential survival regression that adjusts for the baseline characteristic(s) described above. Summaries of the posterior distribution of the 180-day AFS rate (e.g., posterior mean/median, 95% credible interval, posterior probability that $\phi > 0.54$) will be presented.

In these analyses, small sites (contributing < 5 subjects) will be combined into one or more larger pseudo-sites of size ≥ 5 but ≤ 10 . An analysis omitting small sites will also be presented. Descriptive statistics will be presented for all sites.

Heterogeneity analyses across the following factors (in addition to sites) will be conducted in a similar manner:

- US/OUS
- Sex (Male/Female)
- Dialysis status (Yes/No)
- Age (≤ 70 , > 70)
- Diabetes (Type I, Type II, None)
- Race/Ethnicity

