6.5 Predictive Model

This section describes the prediction model that is used to predict the 6-month outcomes for subjects who have not yet reached 6 months. This model enables computation of predictive probabilities that form the basis for the sample size decisions in the Goldilocks design; it also serves as the "imputer's model" in the Bayesian multiple imputation that is used in the final inference.

Outcomes at 6 months are binary and are denoted "E" (for having experienced a primary outcome Event) or "N" (for not having experienced an event). At any analysis, it is expected that some subjects will not have completed 6 months, and the 6-month outcomes for those subjects will be imputed based on a statistical model, as described below.

At the time of analysis, subjects will fall into one of three categories:

- A. Status E or N has been observed at 180 days. For example, subject is known to be event-free at 180 days (N), or subject has had a primary event prior to 180 days and at least 180 days has elapsed since that subject entered the analysis cohort (E). (Note: an event at exactly 180 days will count as an event.)
- B. Subject is known to have had an event at time < 180 days, but the subject has not yet had the opportunity to be followed for 180 days. For example, subject dies at Day 100 but the data cutoff date for analysis is only 25 days later, before the subject has the opportunity to be followed for 180 days.
- C. Subject is censored without known event at time < 180 days.

Subjects in Group A have observed 180-day event status and need no imputation. Subjects in Group B will have their 180-day status set to E (with probability 1). Subjects in Group C will have their 180-day outcome imputed to be E with a probability that is subject-specific and is based on how long that subject has been followed and also on the event-free survival experience of other subjects, calculated via a Bayesian piecewise exponential survival model, as follows.

STATISTICAL ANALYSIS PLAN

In this imputation model, the hazard function $h(\tau)$ is piecewise constant over the intervals $[0, 30 \text{ days}]$, $(30 \text{ days}, 60 \text{ days}]$, $(60 \text{ days}, 90 \text{ days}]$, and $(90 \text{ days}, 180 \text{ days}]$. Specifically, let each subject's time to event be modeled such that the survivor function is

$$S(t) = e^{-\int_0^t h(\tau) d\tau}, \text{ where}$$

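### Fitting the heterogeneity Cox models to completers deletes event-free dropouts but keeps events, so unequal loss to follow-up distorts the site and US/OUS comparisons

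*SAP*

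**What the plan says.** SAP 9.5 and protocol 11.9 specify the site model in the same words: "Based on completers, a (frequentist) Cox proportional hazards regression will be conducted", with a term for site. If the site p-value is above 0.10, "data will be considered poolable across sites". If it is below 0.10, baseline characteristics are examined as an explanation. If they explain the difference, an adjusted Bayesian analysis follows. If they do not, results are shown by site and in groupings of sites, with the example "perhaps removing any markedly different sites". The same approach is then applied to US/OUS, sex, dialysis, age, diabetes and race/ethnicity.

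Neither section defines a completer. The nearest description is the completers-only sensitivity analysis in SAP 9.1.1, which is "based on those subjects whose status is known at Day 180" and leaves out subjects whose final primary outcome is missing.

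SAP 6.5 shows who those subjects are. A known event before Day 180 fixes the Day-180 status as an event. The group whose outcome must be imputed is described as "Subject is censored without known event at time < 180 days". The loss model in SAP 6.7 agrees: "if the event time occurred before the LTFU time, that subject had an observed event at the event time".

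**The concern.** Cox regression exists to use incomplete follow-up, so restricting it to completers gains nothing and discards event-free person-time. The restriction also selects on outcome. Of two subjects who would both drop out on the same day, the one with an earlier event stays in the model and the one without is deleted. The apparent hazard in a group therefore rises with its loss to follow-up, even when the true hazard does not.

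The distortion works both ways. It can suggest a difference between groups that do not differ, and it can mask a real one when the group with more loss is doing better. Because a non-significant result is taken as grounds for pooling, masking gives a poolability claim that the data have not earned. A false signal starts a search for explanatory covariates and possibly displays by site.

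The restriction is also out of line with the rest of the plan. The primary analysis retains event-free dropouts by imputation, and the exploratory Cox models in SAP 9.6 state no such restriction.

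**Working it through.** **Inputs from the documents.** Piecewise hazards, and loss spread uniformly over 180 days at 10% overall (SAP 6.7); maximum N of 105 (SAP 4); threshold p = 0.10 (SAP 9.5).

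**Assumptions.** Loss rates by group, which the documents do not give; group splits of 53/52 and 80/25; dropout unrelated to prognosis.

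**Step 1: reproduce the plan's survival curve.** Cumulative hazard to Day 180 = 30 × (0.005417298 + 0.00647187 + 0.004045362) + 90 × 0.0015350038 = 0.4780 + 0.1382 = 0.6162, and exp(−0.6162) = 0.540. The earlier points come out at 0.850, 0.700 and 0.620. All match SAP 6.7. For true AFS 0.70 the hazards are multiplied by −ln(0.70)/0.6162 = 0.579. The plan states no error rate or power for the heterogeneity test, so there is none to reproduce.

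**Step 2: apparent AFS among completers.** With true AFS φ, loss probability L, and m the average of the event-time distribution function over 0–180 days (0.2021 at φ = 0.70, 0.3180 at φ = 0.54):

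completer AFS = φ(1−L) / [φ(1−L) + (1−φ)(1−L) + L·m]

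Example, φ = 0.70 and L = 0.20: 0.56 / (0.56 + 0.24 + 0.0404) = 0.666.

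| Loss | True AFS 70% | True AFS 54% |
|---|---|---|
| 0% | 70.0% | 54.0% |
| 10% | 68.5% | 52.2% |
| 20% | 66.6% | 50.0% |
| 30% | 64.4% | 47.5% |

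**Step 3: false positives, two groups with identical hazards.** Cox score (log-rank) test at p < 0.10, N = 105, true AFS 70%, 20,000 simulated trials per row. Paired figures are for the 53/52 and 80/25 splits.

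| Loss, group 1 vs 2 | Completers | All, censored | Median HR, completers |
|---|---|---|---|
| 5% vs 15% | 10.6%, 11.4% | 9.8%, 10.3% | 1.07, 1.07 |
| 0% vs 20% | 13.0%, 12.6% | 10.3%, 9.9% | 1.15, 1.14 |
| 5% vs 30% | 14.6%, 14.9% | 10.0%, 10.0% | 1.20, 1.21 |

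With everyone kept, the median HR is 0.99–1.00 in each row. A separate 8,000-trial run at 53/52 gave 11.0%, 12.6% and 14.0% for completers. If losses all fall at Day 30 (as could follow from the 30-day follow-up after a failed or unattempted implant, protocol 5.5), the distortion is smaller: 11.0% vs 10.5% for 0% vs 20% loss.

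**Step 4: a real difference, 0% vs 20% loss.**
- Higher-loss group truly better (HR 0.5): power is 36% with completers and 50% with all subjects (35% and 49% in the separate run). Median HR is 0.58 against 0.51. At 5% vs 30% loss, power is 30% against 49%.
- Higher-loss group truly worse (HR 2.0, separate run): the completers' median HR is 2.24 against 2.00, and the test rejects 82% of the time against 70%. The effect is exaggerated.

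**Step 5: many small sites.** With 13 sites of 8–9 subjects (6,000 trials), completers vs all subjects:
- equal loss: 14.8% vs 14.1%
- half the sites at 0% and half at 20%: 16.1% vs 15.1%
- four sites at 30%: 17.0% vs 13.6%
- two sites at 60%: 25.4% vs 14.0%

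**The case against.** **The definition is inferred.** SAP 9.5 does not say what a completer is. This stands, and the missing definition is part of the point. The other literal reading, only subjects followed event-free to Day 180, would leave no events to model, so the reading used here is much the likeliest.

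**The effect is small at plausible imbalance.** At 5% vs 15% loss, close to the planned 10% on average, false positives rise by about one point. This stands. The larger figures need imbalances that the documents neither predict nor rule out.

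**Site-level noise dominates.** If all 25 sites enrol, the mean is 105/25 = 4.2 subjects, and sites under 5 are merged into pseudo-sites of 5–10. The standard error of a 70% rate in 8 subjects is √(0.7 × 0.3/8) = 16 points, against a 5.6-point gap (70.0% − 64.4%) even at 0% vs 30% loss. This stands for sites. US/OUS is a two-group contrast and is less protected by it.

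**Much is covered elsewhere.** SAP 9.6 fits Cox models with no stated completers restriction for sex, dialysis, age, diabetes and race/ethnicity, and follow-up compliance is tabulated by site. This stands, and narrows the point chiefly to site and US/OUS.

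**A reader might infer that this model can change the trial's main result, or that sites would be dropped.** The documents do not support that. The primary test uses multiple imputation and a beta posterior in the mITT population and does not depend on the site p-value. Removing sites is offered only as a possible display after an unexplained site effect. The completers restriction is attached to the Cox model and is not stated for the follow-on Bayesian regression.

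**Conclusion.** The restriction introduces a real but modest selection bias. Under the assumed loss rates, it raises a nominal 10% two-group test to about 11–15% and can cut power from about 50% to about 35% when the higher-loss group truly does better. Masking is the more consequential direction, because a non-significant result supports pooling.

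The reach is limited to the poolability statement and its follow-on analyses. These sizes rest on assumed group-specific loss, dropout unrelated to prognosis and the SAP's own hazards. Informative dropout would bias a censored Cox model too.

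It would also be wrong to conclude that removing the restriction gives a 10% test across sites: with many small sites the test rejects about 14–15% of the time under equal loss with either analysis set. Severity is minor and confidence medium.

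**What to change.** In SAP 9.5 and protocol 11.9, replace the completers phrase with: *In all mITT subjects, censored at last contact or Day 180*. Apply it to site, US/OUS and the other listed factors. Define a completer as a subject whose Day-180 status is known, and keep that version only as a sensitivity analysis. State that the censored model assumes non-informative dropout, and report loss to follow-up by site and by US/OUS beside the results.

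The cost is one phrase in each document plus a definition. No new data are needed, and the primary analysis does not change. The small-site inflation needs separate handling, for example a caution when the many-site p-value is interpreted.
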